A lack of expertise of primary care providers in the assessment of risk and difficulty linking patients to needed resources may also pose significant barriers for providers in screening processes. Integrated tools for risk assessment and referral for follow-up of positive IPV screening, including reminders of legal conditions that may mandate disclosure (for example, children witnessing IPV events), may help providers feel more comfortable with screening tasks [5, 10], and thus encourage compliance with screening guidelines. While screening and counseling for IPV is a billable activity, the desire to keep discussions private may result in a provider not using IPV-related billing codes and losing potential credit for time spent counseling in provider productivity calculations. An approach to document time spent in confidential activities that a health system might *choose not to bill for* because of privacy concerns may be important positive reinforcement for provider screening behaviors for IPV.

The objective of this paper is to describe the protocol of a stepped wedge cluster randomized trial for evaluating the effectiveness an IPV screening workflow consisting of three major components:

1. a non-interruptive alert for annual IPV screening;
2. PVS confidential screener;
3. Provider risk assessment of PVS screening results and patient referrals.

Stepped wedge study design was chosen for several reasons [11]. Firstly, we had a background control condition present (nurse-led screening) in all clinics. Secondly, because each cluster acts as its own control we need a limited set of clusters to reach the desired level of statistical power. We also needed time to do staff trainings and intervention support, and make sure that they follow our intervention protocol, with stepped wedge design we could do trainings in 5 clinics at a time. In addition, this design gives us control over temporal trends in the data.

METHODS/DESIGN

Study design/Participants

The protocol for this study is based on a stepped wedge cluster randomized controlled trial design [12].

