The self-reported questionnaire approach is to maximize potential patients' willingness to report for IPV [14]. Because of the difficulties in ensuring a tablet computer or other device will be available in all primary care settings and in ensuring the privacy of responses after patient use, we will develop the kiosk-style approach: the medical assistant assures the patient is alone by removing another adult-age family from the room, so that the patient can use exam computer to give response to a 3-item PVS initial screening questionnaire [15], which if positive, will cascade to an additional questionnaire administered to assess risk levels of future harm [16]. The approach provides the maximum feasible level of protection for the privacy of patients' responses. Completion of the questionnaires results in a lock screen for the computer while awaiting the provider's portion of the visit. If the patient has screens positive for IPV, a popup alert notifies the provider. Clicking on the "IPV navigator Activity" in the alert takes the provider to an electronic form that provides decision support for IPV care.

The IPV Visit Navigator is a decision support tool that displays patients' responses to screening questions, helps the provider further evaluate a patient's risk level, offers recommended follow-up questions with examples of scripted responses, supports documentation of an IPV specific physical examination, and of counseling. It also allows the provider to record time spent on this issue during the visit to allow potential credit for this time in resource valuation units (RVUs) without billing, which might compromise privacy. The results are stored in an electronic flow sheet hidden from other visit records. Providers then complete reassessments of risk, physical exam findings, and document follow-up recommendations. On return visits, a Blocking BPA reminds providers to access the Navigator to review data. All patients screened positive are automatically reassessed on their next clinic visit for risk.

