Based on our current practice visit patterns for unduplicated visits by women between age 18 and 49 years, we will have approximately 34,000 eligible visits during the non-screening steps and 34,000 during the screening steps. We have assumed an annual IPV prevalence of 5.5% within the preceding year, based on rates reported by the CDC for SC [17], a screening completion rate of 95%, a 75% counselling rate for women who screen positive, and a 50% referral rate to the Hotline. Studies report the ability of screening to increase patient referral to services from a 2.5 percentage point to an 8.0 percentage point increase based on current referral rates between 0% and 3.6% [18]. Based on an analysis of our archival data, we expect that our current referral rate for IPV for women aged 18-49 seen in our clinics is no more than 0.14% and that this rate will increase to 3.9% with screening.

With about 600 relevant patient visits over 6 months per clinic, 8-12 clinics per wedge, and 3 wedges, we estimate that we will have 97% power to detect an increase in screening (i.e. 0.14% vs. 5.5%), and 89% power to detect a difference in the rate of referral for counseling and/or calls to the Domestic Violence Hotline (i.e. 0.14% vs. 3.9%). While we may be somewhat overpowered for our primary analysis, these numbers of clinics and patients will also allow us to make very precise estimates of the treatment effects within relevant patient subgroups (e.g. whites vs. blacks, urban vs. rural) and to determine whether there are any differential impacts of the intervention on those subgroups. These power calculations are conducted using PASS15 (NCSS, Kayesville, UT) and verified using the 'steppedwedge' function in STATA (StataCorp, College Station, TX), assumed an intraclass correlation coefficient of 0.05 (to account for a moderate level of clustering of patients within clinics), along with an alpha of 0.05 and two-sided testing.

Statistical analysis

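### The powered referral contrast (0.14% vs 3.9%) has no common measure across conditions: the dedicated counselling and follow-up record arrives with the intervention, so an observed rise may partly reflect recording

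*Combined protocol and SAP*

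**What the plan says.** All references are to the combined protocol and SAP.

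- **Power Calculations.** The control rate rests on archival data: "we expect that our current referral rate for IPV for women aged 18-49 seen in our clinics is no more than 0.14" per cent. The plan expects that "this rate will increase to 3.9% with screening". It claims "89% power to detect a difference in the rate of referral for counseling and/or calls to the Domestic Violence Hotline (i.e. 0.14% vs. 3.9" per cent). It does not say which records or fields the archival analysis used.
- **Background.** The wish to keep discussions private "may result in a provider not using IPV-related billing codes and losing potential credit for time spent counseling". The plan presents a way to document confidential time as possible positive reinforcement for providers.
- **Study design/Participants.** The control record is a nurse checklist of abuse/neglect findings. No field for referral or counselling is described.
- **Intervention.** The IPV Visit Navigator, opened from an alert after a positive screen, supports documentation of counselling and follow-up recommendations. "It also allows the provider to record time spent on this issue during the visit to allow potential credit for this time", without billing. "The results are stored in an electronic flow sheet hidden from other visit records".
- **Data Sources/Collection.** All data come from Epic.
- **Outcome measurement and Statistical analysis.** Referral is among the other outcomes, as a share of women who screened positive, and those outcomes are to be analysed largely descriptively.

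**The concern.** Before a clinic switches, a referral or counselling episode can be found only in ordinary Epic records. After the switch there is a purpose-built place to record it, hidden from other visit records, with potential credit for the time. The opportunity and the incentive to record both change at the moment the treatment changes.

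The planned model cannot separate the two. The step effects absorb calendar changes shared by all clinics, and the random clinic effect absorbs stable differences between clinics. A recording change tied to each clinic's own switch coincides with the treatment indicator. The listed sensitivity analyses cover early versus late randomization, learning, IPV champions, screening refusal, counselling acceptance and missing data. None varies how completely control-period referrals are captured.

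If the final report sets intervention-period referrals against 0.14%, or against control-period counts from ordinary records, care that was given but not recorded before the switch would be credited to the intervention. Such a comparison is foreseeable. The plan powers it, and Discussion names the link between screening and the start of counselling as a critical evidence gap.

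**Working it through.** **1. Reproduce the stated power.** Inputs from Power Calculations: 34,000 visits per condition, 28 clinics, intraclass correlation 0.05, two-sided alpha 0.05. Treat the data as a parallel comparison with 14 clinics' worth per condition:

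- m = 34,000 / 14 = 2,429 visits per clinic
- design effect = 1 + (2,429 − 1) x 0.05 = 122.4
- effective n = 34,000 / 122.4 = 277.8 per condition
- power for 0.14% vs 5.5%: 97.0% (stated 97%)
- power for 0.14% vs 3.9%: 88.5% (stated 89%)

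A Hussey-Hughes stepped-wedge calculation (28 clinics, 4 periods, 600 visits per clinic-period) gives about 100% for both, so it is not the source of the stated figures.

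**2. Where 3.9% comes from.** The plan's assumed prevalence, screening completion and counselling rates give 5.5% x 95% x 75% = 3.92%. That is a projected counselling rate. The figure it is compared with, 0.14%, is called a referral rate. Using the plan's 50% Hotline referral rate instead:

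- 50% of screen-positives: 5.5% x 95% x 50% = 2.6%; power 71% by the method of step 1
- 50% of those counselled: 3.92% x 50% = 2.0%; power 56%

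**3. Effect of incomplete control capture.** Let c be the share of true control-period events visible in the archival data. The documents give no value, so c is an assumption shown over a range. Hold 3.9% as fully captured.

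- true control rate = 0.14% / c
- share of the rise due to recording = (0.14%/c − 0.14%) / (3.9% − 0.14%)
- odds ratio = (0.039/0.961) / (p0/(1 − p0)), where p0 is the true control rate

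| c | True control rate | True rise (points) | Share due to recording | Odds ratio | Power (step 1 method) |
|---|---|---|---|---|---|
| 100% | 0.14% | 3.76 | 0% | 28.9 | 88.5% |
| 50% | 0.28% | 3.62 | 3.7% | 14.5 | 84.9% |
| 25% | 0.56% | 3.34 | 11.2% | 7.2 | 76.1% |
| 10% | 1.40% | 2.50 | 33.5% | 2.9 | 45.0% |

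Example, c = 50%: (0.28 − 0.14)/3.76 = 3.7%; odds 0.0406/0.00281 = 14.5.

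Recording alone would explain the whole rise only at c = 0.14/3.9 = 3.6%. Under the Hussey-Hughes calculation, power stays at or above 99% down to c = 5%, so interpretation is more at risk than power.

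The two scales behave differently. The difference in points barely moves until capture is low, but the odds ratio, the scale of the planned logit model, halves at 50% capture because the baseline is so rare.

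**The case against.** Several points on the other side are sound.

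- **The plan does not say that clinicians leave IPV care uncoded.** A reader might infer it from Background, but the sentence is conditional and concerns billing codes, not referrals or documentation in general. Nothing says that the 0.14% was built from codes or that it missed events.
- **The projected rise from 0.14% to 3.9% is not itself a recording artefact.** A reader might infer that too, but 3.9% matches a product of assumed rates and no Navigator entry went into it. Unequal recording could affect only the 0.14% and a contrast observed later.
- **The outcome and analysis sections specify no test of referral between conditions.** Referral is a descriptive share of screen-positives. This stands, and it narrows the point: Power Calculations powers a contrast that those sections do not define.
- **Large distortion needs very low capture.** A true control rate of 1.40% would mean 1.40/5.5 = 25% of prevalent cases already being referred or counselled, under a judgement-based checklist. The plan cites current referral rates elsewhere of 0% to 3.6%, so this is possible, but nothing local supports it.
- **Crediting the intervention only with what remains after Navigator entries are removed would be wrong.** The hidden flow sheet and the confidential department may draw documentation out of ordinary records after the switch. A contrast without those entries could approach zero even if the intervention works.

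What remains is that recording differs by condition, the baseline source is undescribed, and a between-condition contrast is powered with no safeguard.

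**Conclusion.** The point holds in a limited form. The plan powers a referral contrast for which it defines no common measure, and the dedicated record exists on one side only. An observed rise over 0.14% may partly reflect recording, in the intervention's favour, by an amount the documents do not allow one to estimate. Under assumed control capture of 50%, 25% or 10%, with 3.9% taken as fully captured, recording explains about 4%, 11% or 34% of the rise in points, and the odds ratio falls from 29 to about 14, 7 or 3.

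Separately, a projected counselling rate is set against a referral baseline, and the powered contrast does not match the descriptive outcome, whose denominator is screen-positives. Power Calculations, Outcome measurement and Statistical analysis must be reconciled. The primary outcome, completion of the PVS questions, is unaffected.

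**What to change.** State how the 0.14% was derived: which records, which fields, which denominator. Then choose one of two routes.

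(a) Drop the powered referral contrast. Report Navigator referrals as a description of the intervention period, as Statistical analysis largely does already, and do not set them against 0.14%.

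(b) If conditions are to be compared, fix one definition (referral or counselling, not a mixture), one denominator (all eligible women) and the same Epic sources in all four periods. Show the contrast with and without Navigator-only entries as two bounds, stating that the version without them is biased against the intervention. Add a sensitivity analysis over the assumed control-period capture rate, on both the difference and odds-ratio scales, and redo the power statement for the measure chosen.

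Route (a) costs only wording. Route (b) costs one more Epic extraction, and a referral estimate that may be less favourable or span a wider range.

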Methods/Design: A stepped wedge cluster randomized trial across the 28 clinics in three blocks of 8-12 sites will be used to assess the impact of an electronic health record (EHR)-based multifactorial intervention screening for Intimate Partner Violence in primary care practice for women aged 18 to 49 years. Our EHR intervention will promote IPV screening and risk management in primary care and will consist of three components: (1) a non-interruptive EHR alert; (2) confidential screening using the 3-item Partner Violence Screening (PVS) instrument and (3) confidential assessment and referral of high-risk patients using decision-support templates. Efficacy of each of these components will be assessed separately. The trial will be conducted in the setting of a control intervention of screening for IPV using nurse interviews and an electronic checklist.

Discussion: This paper describes the use of a stepped wedge cluster randomized trial to evaluate a privacy preserving screening approach.

BACKGROUND

Intimate Partner Violence (IPV) is a frequently occurring condition (5.9% annual rate of IPV reporting in women in US [1]) for which screening in primary care is the United States Preventative Service Task Force recommended service [2]. The lifetime prevalence of IPV is reported to be 25% of all women [3].

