28 clinics (14 Family Medicine, 12 Internal Medicine Primary Care and 2 women's health clinics) are grouped into 3 blocks each holding 8-12 clinics based on number of eligible patients seen in 2018-2019 and the number of full-time employees in clinics to assure that each block has similar population and employee size. We then use random number generator to randomize the starting time for 3 blocks. The target population is all women aged 18-49 who visit the clinics during the whole study period. Multiple screenings of the same patient can be made as it is described in the Intervention section. The blocks are shown in Figure 1.

Control (nurse-led screen)	Intervention Start (nurse-led and confidential screen)		
Time Period 0	Time Period 1	Time Period 2	Time Period 3

Q1 2020 – Q2 2020	Q3 2020 – Q4 2020	Q1 2021 – Q2 2021	Q3 2021 – Q4 2021
28 clinics	8-12 clinics 16-20 clinics	16-20 clinics	28 clinics

Figure 1. Randomized Stepped Wedge design with 28 clinics.

The control condition is a nurse-led screen developed by MUSC and deployed in 2019. When patients are roomed in all outpatient clinics, nurses complete a checklist where they, based on professional judgment (e.g., without asking standardized questions), screen for a variety of factors. One of those factors is Abuse/Neglect. Clicking on this item in the Epic EHR user interface, opens a second menu for nurses to document either the absence of any evidence of abuse/neglect or the presence of different risk factors. Selecting the “caregiver degrades or threatens patient”, “abuse/neglect suspected”, “evaluation for abuse”, “excessive fear/withdrawn or guarded behavior” or “has unexplained injuries or bruises” was considered a positive screener for spousal abuse risk. It is important to note that control screening is always present (though not necessarily completed) when patient is eligible for confidential screening intervention, thus two screens are working at the same time during intervention period.

IRB determined that this was a quality improvement effort which did not require consent identifying and managing IPV is part of current practice the intervention was the Epic automatic fielding and special protection approaches used that decreased patient risk of disclosure.

Intervention

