Table 1. How IPV Positive patients were identified using both screens.

Screen type	IPV Positive	IPV Negative
Nurse-led screening	
One or several of the following answers is selected by during assessment for Abuse/neglect:
 
• Has unexplained injuries, bruises, cuts• Caregiver degrades or threatens patient• Abuse/neglect suspected• Being evaluated for suspected abuse	
One or several of the following selected:
 
• No suspicion of abuse or neglect• Poor hygiene, dirty/unkept inappropriate clothing• Excessive fear, withdrawn, or guarded behavior• Non-compliance with plan of care
Confidential screening	
In case one of the following answers was given:
 
• Have you been hit, kicked, punched, pushed, shoved, or otherwise hurt by someone at home in the past year? Yes• Do you feel safe in your current relationship? No• Is there a partner from a previous relationship who is making you feel unsafe now? Yes	
In case when the following answers were given:
 
• Have you been hit, kicked, punched, pushed, shoved, or otherwise hurt by someone at home in the past year? No• Do you feel safe in your current relationship? Yes, or Not applicable.• Is there a partner from a previous relationship who is making you feel unsafe now? No

Power Calculations

This study will involve a total of n=28 clinics which will provide two years of data on approximately 68,000 patient visits. Of these, we expect 34,000 to occur during the non-screening steps and 34,000 visits during the intervention period.

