We will use a generalized linear mixed model with a logit link controlling for block set and a fixed effect for each step, as discussed by Hussey and Hughes [19], to compare active screening accounting for the cluster design with a random clinic effect. Primary analyses will also adjust for patient characteristics (age, race) since these have been associated with risk of IPV. Models will be estimated with interaction terms to assess subgroup effects for specific patients, and to examine the effect of practices' characteristics on the heterogeneity of the estimates.

The intraclass correlation coefficients will also be estimated and reported for screening and counselling to assess the assumptions made for the sample size analyses so that this information will be available to future investigations using similar designs and outcomes.

Analysis for the other outcomes will be largely description. Frequency tables with patient demographics, including race, insurance, ethnicity, age, and marital status will be reported. Responses to individual PVS questions will also be presented in the form of frequency tables. Danger 5 risk assessment will be presented using histogram showing counts of patients that scored 0 to 5 of the risks [16]. Physician compliance will be measured as percentage of screened positive patients for whom decision-support templates have been based. Rates of referrals will be reported as percentage from total of patients screened positive.

In addition, we will perform sensitivity analyses to assess the effects of early vs. late randomization, potential “learning” effects that may occur as the screening becomes better integrated in practice routines, the effect of the practices’ presence of a IPV champion prior to the study, and the effect for practice-specific screening refusal and rate of counselling acceptance on the overall estimate. Sensitivity analyses for the primary and secondary outcomes will be conducted using several methods, which have different missing data assumptions: 1) Complete case analyses which assumes missing data are completely at random; 2) Multiple imputation using $M=10$ imputations, which assumes missing at random; and 3) Assigning contrasting age group, race and income category classifications for missing values differentially by intervention group, which aligns with non-ignorable missingness (the data missingness is nonrandom and related to the actual values.)

Follow-up interview

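### The stated 97% and 89% power are not what the planned stepped wedge gives on the stated inputs; the figures look conservative and their method and inputs should be stated

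*Combined protocol and SAP*

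**What the plan says.** The Abstract describes "A stepped wedge cluster randomized trial across the 28 clinics in three blocks of 8-12 sites", and the diagram under Study design/Participants has all 28 clinics in control in period 0 and all in intervention by period 3. The Power Calculations section gives the volume: "This study will involve a total of n=28 clinics which will provide two years of data on approximately 68,000 patient visits", of which "we expect 34,000 to occur during the non-screening steps and 34,000 visits during the intervention period". It then sets out the cell size, "With about 600 relevant patient visits over 6 months per clinic, 8-12 clinics per wedge, and 3 wedges", and concludes "we estimate that we will have 97% power to detect an increase in screening (i.e. 0.14% vs. 5.5%), and 89% power to detect" (the second comparison being referral, 0.14% vs 3.9%). One ICC of 0.05 and a two-sided alpha of 0.05 are given. The figures are attributed to PASS15 and described as "verified using the 'steppedwedge' function in STATA".

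Under Statistical analysis, the model is a logit mixed model with a random clinic effect, "controlling for block set and a fixed effect for each step, as discussed by Hussey and Hughes".

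**The concern.** In a stepped wedge with a random clinic intercept, each clinic is its own control, so most of the between-clinic variation drops out of the treatment comparison. With 600 visits per clinic-period and differences of 5.4 and 3.8 percentage points (pp) from a near-zero baseline, power should be close to 100%. Figures of 97% and 89% are the size expected when between-clinic variation is carried in full, as in a parallel cluster trial.

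At stake is whether the power statement describes the design and model that will be used, and whether a reader can reproduce the stated check. The plan also intends to report observed ICCs so that the sample-size assumptions can be assessed. That needs a calculation whose structure is known.

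**Working it through.** **Inputs.** From Power Calculations: 28 clinics, 68,000 visits (34,000 per condition), 600 visits per clinic per 6 months, 3 wedges, ICC 0.05, two-sided 0.05, rates 0.14% vs 5.5% and 0.14% vs 3.9%. From Study design/Participants: 4 periods and 8-12 clinics per block, taken here as 9/9/10. Check: 28 × 4 × 600 = 67,200 visits. Throughout, power = Φ(z − 1.96) with z = difference/SE, and pairs are given as 5.5% comparison / 3.9% comparison.

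**Reproducing the printed figures.** Treat the visits as two parallel arms of 14 clinics.

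- Visits per clinic: 68,000/28 = 2,429. Design effect: 1 + (2,429 − 1) × 0.05 = 122.4. Effective n per arm: 34,000/122.4 = 277.8.
- 0.14% vs 5.5%: SE = √[(0.0014×0.9986 + 0.055×0.945)/277.8] = 0.01386; z = 0.0536/0.01386 = 3.87; power 97.2%.
- 0.14% vs 3.9%: SE = 0.01183; z = 0.0376/0.01183 = 3.18; power 88.8%.

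With 600 visits per clinic instead of 2,429, a pooled-variance version gives 96.7% and 87.8%.

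**Stepped wedge on the same inputs.** The Hussey-Hughes variance is

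Iσ²(σ² + Tτ²) / [(IU − W)σ² + (U² + ITU − TW − IV)τ²],

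with I = 28 and T = 4. For 9/9/10 clinics crossing over at periods 1, 2 and 3:

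- U = 27 + 18 + 10 = 55; W = 0² + 9² + 18² + 28² = 1,189; V = 9×9 + 9×4 + 10×1 = 127.
- Average rate 0.0282, total variance 0.0282 × 0.9718 = 0.02740; τ² = 0.05 × 0.02740 = 0.001370; σ² = 0.95 × 0.02740/600 = 0.0000434.
- Numerator: 28 × 0.0000434 × 0.005524 = 6.71×10⁻⁶. Denominator: 351 × 0.0000434 + 873 × 0.001370 = 1.211. Variance 5.54×10⁻⁶, SE 0.00235.
- z = 0.0536/0.00235 = 22.8. For 3.9% the SE is 0.00200 and z = 18.8. Power exceeds 99.9% for both.

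**Does the result depend on details the plan leaves open?** All rows use 600 visits per cell and generalised least squares. Variance is at the average rate except in the condition-specific rows and the last row.

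| Variance structure | SE, pp | z | Power |
|---|---|---|---|
| One clinic intercept | 0.24 / 0.20 | 22.8 / 18.8 | >99.9% / >99.9% |
| Plus block effects | 0.24 / 0.20 | 22.7 / 18.8 | >99.9% / >99.9% |
| Block effects, autocorrelation 0.8 | 0.64 / 0.54 | 8.4 / 6.9 | >99.9% / >99.9% |
| Block effects, autocorrelation 0.5 | 0.97 / 0.82 | 5.5 / 4.6 | 99.98% / 99.6% |
| ICC 0.05 within each condition, clinic effects correlated 1 | 0.83 / 0.68 | 6.4 / 5.5 | >99.9% / 99.98% |
| Same, correlated 0 | 1.00 / 0.86 | 5.4 / 4.4 | 99.97% / 99.3% |
| Block effects, autocorrelation 0 | 1.35 / 1.14 | 4.0 / 3.3 | 97.8% / 90.7% |
| Block effects, autocorrelation 0.5, variance at the intervention rate | 1.33 / 1.13 | 4.0 / 3.3 | 98.1% / 91.4% |

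Further checks with a single clinic intercept: reading 600 as a clinic's total (150 per period) gives z of 11.5 and 9.5; ICCs from 0.001 to 0.2 keep z above 18; a logit-scale approximation to the planned model gives 17.5 and 15.5. Under that simple structure, power of 97.0% and 88.8% would need about 15 visits per clinic-period.

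**The case against.** **The simple Hussey-Hughes SE is too small to rely on.** This stands. With one additive intercept and variance at the average rate, the clinic SD is √0.001370 = 3.7 pp around a control rate of 0.14%, which would put many clinics below zero. Applying ICC 0.05 within each condition gives clinic SDs of 0.84 pp under control and 5.1 or 4.3 pp under intervention, and the clinic effects no longer cancel. A reader might infer from 1.39 against 0.24 pp that the printed power implies SEs about six times those of the real design. The documents do not support that as a general statement: under condition-specific variance the ratio is only about 1.4 to 1.7.

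**The sponsor may have allowed for more variation.** Possibly. The last two table rows come near the printed pair. They require zero autocorrelation with block effects, or autocorrelation 0.5 combined with block effects and the larger variance. The plan states one ICC and neither an autocorrelation nor a variance convention.

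**The match does not prove the method.** This also stands. A reader might infer that a parallel formula was used. With the rates fixed, both powers follow from one effective sample size, so matching both is largely one match. A t-test version on 26 df gives about 96% and 86%. The PASS and Stata inputs are not in the documents.

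**Nothing turns on it.** Largely fair. Power is understated, and the section already concedes that the primary analysis may have more power than it needs. A reader might also infer that the subgroup claim falls with these figures. It does not: the text rests subgroup precision on the numbers of clinics and patients, and higher power would help it.

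**Conclusion.** The point holds as a correction to the power statement. On the stated inputs, the cited method gives above 99.9% for both comparisons, not 97% and 89%. Condition-specific clinic variance, or autocorrelation of 0.5 or more with variance at the average rate, gives at least about 99%. The lowest of these is the referral comparison at 99.3%, or 98.7% with a t reference on 22 df. Lower values need stacked assumptions that are not in the plan.

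These results assume about 600 visits per cell, four periods, roughly equal blocks and the rates as printed. Whether those rates represent the primary outcome is a separate question. The agreement with a 14 vs 14 parallel calculation is an observation, not evidence of how the figures were produced. The discrepancy is conservative: clinic numbers, visit numbers and the analysis are unaffected.

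**What to change.** In Power Calculations, replace the two figures with power for the 3-sequence, 4-period stepped wedge with 28 clinics and about 600 visits per clinic-period, under the model in Statistical analysis. Simulation from the logit mixed model is preferable, because linear approximations fit poorly at a control rate of 0.14%. State the clinic variance structure (common or condition-specific) and a cluster-autocorrelation range such as 0.5 to 1. Report the SE as a range across these structures, not as the single values 0.24 and 0.20 pp.

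For the verification statement, give the actual PASS and Stata inputs, or say that the printed figures are a conservative parallel approximation. Use the same calculation for any outcome rates that are later corrected.

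The cost is a short recalculation and a wording change. Sites, patients and procedures do not change.
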